Subjects who discontinue treatment due to lack of efficacy or to an AE prior to 12 weeks following achievement of a platelet count of at least 50,000/ μ L, will be considered failures. The null and alternative hypotheses for the comparison of fostamatinib vs. placebo are as follows:

$$H_0: p_F = p_P \quad \text{vs.} \quad H_1: p_F \neq p_P$$

where p_F and p_P denote the true proportions achieving and maintaining a stable platelet count for fostamatinib and placebo, respectively. The null hypothesis will be tested using a 2-sided

McNemar's test conducted with a significance level of 0.05. This analysis will be performed for the Treated and Per Protocol populations.

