### 4.3. Primary Efficacy Endpoint

**Version 1:** The first version of the primary efficacy endpoint is for the purpose of assessing efficacy among all patients while they are on active treatment in one of the prior studies, in the current extension study, or in both. This version of the primary efficacy endpoint is the achievement and maintenance of a stable platelet response defined as follows:

- 1) Achievement of a platelet count of at least 50,000/ $\mu$ L within 12 weeks of beginning active treatment and
- 2) Achievement of a sustained stable platelet response; defined as no two visits, at least 4 weeks apart, with a platelet count < 50,000/  $\mu$ L, without an intervening visit with a platelet count of  $\geq$  50,000/  $\mu$ L unrelated to rescue therapy, within a period of 12 months following initial achievement of the target platelet count (see above).

The beginning of active treatment may be in the prior study or in the present extension study, depending upon when the patient first received active treatment. Patients who discontinue treatment due to lack of efficacy or to an AE prior to 12 months following achievement of a platelet count of at least 50,000/ $\mu$ L will be considered failures.

**Version 2:** The second version of the primary efficacy endpoint is for the purpose of a within-patient, between-study comparison of fostamatinib and placebo among patients randomized to placebo in either of the prior studies, This version of the primary efficacy endpoint is the achievement and maintenance of a stable platelet response defined as follows:

- 1) Achievement of a platelet count of at least 50,000/ $\mu$ L within 12 weeks of beginning treatment (placebo treatment in the prior study and fostamatinib treatment in the present study) and
- 2) Achievement of a sustained stable platelet response; defined as no two visits, at least 4 weeks apart, with a platelet count < 50,000/  $\mu$ L, without an intervening visit with a platelet count of  $\geq$  50,000/  $\mu$ L unrelated to rescue therapy, within a period of 12 weeks following initial achievement of the target platelet count (see above).

Platelet counts taken within 28 days of rescue therapy will be excluded when determining the value of this endpoint. Patients who discontinue treatment or patients who are rescued prior to 12 weeks following achievement of a platelet count of at least 50,000/ $\mu$ L, will be considered failures.

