#### 4.4. Secondary Efficacy Endpoints

The secondary efficacy endpoints are as follows:

- The duration of platelet response (months) and total duration of platelet response (months)
- Patients with reduction in the dose of concomitant ITP therapy while maintaining an adequate platelet count (yes/no)

Duration of platelet response will be defined as the length of time from when the patient first achieves a platelet count of at least 50,000/ $\mu$ L until the first of two visits with platelet counts < 50,000/ $\mu$ L that are at least 4 weeks apart without an intervening visit with a platelet count  $\geq$  50,000/ $\mu$ L unrelated to rescue therapy.

Four additional definitions of duration of platelet responses are stated in **Appendix 14.2**

Patients who drop out of the study before achieving a platelet response (i.e., achieving a platelet count of  $\geq$  50,000/ $\mu$ L) will be assigned a value of 0 for this endpoint. Patients who drop out of the study by the time of database lock while still maintaining a platelet response will be censored as of the time of the last platelet measurement prior to dropping out of the study. Similarly, patients who remain in the study by the time of database lock while still maintaining a platelet response will be censored as of the time of the last platelet measurement prior to the time of database lock. For patients who have achieved and are maintaining a platelet response but who have discontinued treatment due to lack of efficacy or to an AE by the time of database lock, duration of platelet response will be defined as the time from first achieving a platelet count of  $\geq$  50,000/ $\mu$ L until discontinuation of treatment.

The total duration of platelet response is defined as the sum of all durations of platelet responses.

Regarding the secondary efficacy endpoint of patients with reduction in the dose of concomitant ITP therapy while maintaining an adequate platelet (yes/no), a patient is said to have reduction while maintaining an adequate platelet count if the date of reduction of dose of concomitant ITP therapy occurs within the span of the duration of a platelet response during the C-935788-049 study and the reduction was not prompted by AE.

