## **5.0 STATISTICAL METHODS**

### **5.1 General Considerations**

The statistical analysis for this study will be performed using SAS® version 9.4 or higher. All one-sided statistical tests will be performed at the 0.025 significance level, and all two-sided tests will be performed at the 0.05 significance level, unless otherwise indicated.

Prior study treatment group will refer to the patient's randomized treatment group (fostamatinib or placebo) from the previous study in which the patient participated. Unless otherwise specified.

Analyses will be based on only the data from the present study (C935788-049), except for the baseline value and a few other exceptions (e.g., duration of platelet response, primary efficacy endpoint, and the platelet count by-visit summary).

Data collected in this study will be documented using summary tables and patient data listings. Continuous variables will be summarized using descriptive statistics, specifically the mean, median, 25th percentile (Q1), 75th percentile (Q3), standard deviation, minimum and maximum. Categorical variables will be summarized using frequencies and percentages.

Data listings will be sorted by prior study treatment group and patient ID number. All date fields will be presented in a format of ddmmyyyy (i.e., 01Jan2014) in the listings. All data will be included in the data listings.

As a global note, platelet counts taken within 28 days of rescue therapy will be excluded from any platelet count related analyses.

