## 10.0 EFFICACY ANALYSES

### 10.1 Primary Efficacy Endpoint

#### 10.1.1 Version 1

The first version of the primary efficacy endpoint is defined in **Section 4.4** and applies for all patients entering C-935788-049 study. It will be summarized using counts and percentages, together with a 95% exact (Clopper-Pearson) confidence interval for the true percentage of Version 1 responders.

#### 10.1.2 Version 2

The second version of the primary efficacy endpoint is defined in **Section 4.4** and applies for all patients randomized to placebo in either C-935788-047 or C-935788-048 studies and entering C-935788-049 study.

These endpoints will be summarized based on a shift table (**Table 3** below) presenting shifts in responder status from placebo treatment in the C-935788-047 or C-935788-048 studies to fostamatinib treatment in the C-935788-049 study using counts and percentages, together with 95% exact (Clopper-Pearson) confidence intervals for the true percentage of Version 2 responders. In addition, the following hypothesis test will be conducted:

$H_0: P_{01} - P_{10} = 0$  vs.  $H_a: P_{01} - P_{10} \neq 0$ ,

Where  $P_{01}$  denotes true proportions of non-responders from placebo patients in C-935788-047 or C-935788-048 studies who become Version 2 responders in C-935788-049 study and

$P_{10}$  denotes true proportions of stable responders from placebo patients in C-935788-047 or C-935788-048 studies who become Version 2 non-responders in C-935788-049 study.

here  $P_{01}$  and  $P_{10}$  are estimated by  $\frac{c}{a+b+c+d}$  and  $\frac{b}{a+b+c+d}$ , respectively, where a, b, c and d are number of patients as defined in **Table 3** below

**Table 3.** Shift of Response Status For Version 2 Response

Placebo Patients in C-935788-047 or C-935788-048 Studies Who Entered C-935788-049 Study

		Version 2 Responders in C-935788-049 Study		
		Yes	No	Total
Stable Responder in C-935788-047 or C-935788-048 Studies	Yes	a	b	a+b
	No	c	d	c+d
	Total	a+c	b+d	a+b+c+d

The p-value of the null hypothesis test for  $H_0: P_{01} - P_{10} = 0$  will be calculated using a 2-sided exact McNemar's test with a significance level of 0.05. The 95% confidence intervals for the difference in proportion of  $P_{01} - P_{10}$  will be calculated using normal approximation method.

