### 10.2.1 Duration of Platelet Response

Duration of platelet response is defined in **Section 4.4**. It will be analyzed using the Kaplan-Meier method, and the Kaplan-Meier estimate of the median duration of platelet response will be presented together with the 95% confidence interval for the true median. The descriptive summary for the duration of platelet response will also be presented with number (n) of patients with non-missing duration of platelet response and mean/ standard deviation (SD)/ 25th percentile/ median/ 75th percentile/ minimum/maximum of duration of platelet response.

In addition, the duration of platelet response will also be analyzed for the following subgroups of patients:

- C-935788-047 or C-935788-048 fostamatinib subjects who were C-935788-049 primary efficacy endpoint version 1 responders
- all C-935788-049 primary efficacy endpoint version 1 responders
- C-935788-047 or C-935788-048 placebo patients who were C-935788-049 primary efficacy endpoint version 2 responders.

The same analyses as mentioned above will be conducted for the duration of platelet response based on the additional definitions as mentioned in **Appendix 14.2**.

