## 14.2 Additional Definitions of Duration of Platelet Response and Total Duration of Platelet Response

The additional definitions of duration of platelet responses are presented as follows:

- 1) The length of time from when the patient first achieves a platelet count of at least 50,000/ $\mu$ L until the loss of platelet response, which is defined as the earlier time of (the first of two consecutive visits with platelet counts < 30,000/ $\mu$ L that are at least 4 weeks apart or the first use of rescue therapy after first achieving a platelet count of at least 50,000/ $\mu$ L)
- 2) The length of time from when the patient first achieves a platelet count of at least 50,000/ $\mu$ L until the loss of platelet response, which is defined as the earlier time of (the first of two consecutive visits with platelet counts < 20,000/ $\mu$ L that are at least 4 weeks apart or the first use of rescue therapy after first achieving a platelet count of at least 50,000/ $\mu$ L)
- 3) The length of time from when the patient first achieves a platelet count of at least 30,000/ $\mu$ L until the loss of platelet response, which is defined as the earlier time of (the first of two consecutive visits with platelet counts < 30,000/ $\mu$ L that are at least 4 weeks apart or the first use of rescue therapy after first achieving a platelet count of at least 30,000/ $\mu$ L)
- 4) The length of time from when the patient first achieves a platelet count of at least 30,000/ $\mu$ L until the loss of platelet response, which is defined as the earlier time of (the first of two consecutive visits with platelet counts < 20,000/ $\mu$ L that are at least 4 weeks apart or the first use of rescue therapy after first achieving a platelet count of at least 30,000/ $\mu$ L)

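### Version 1 of the primary efficacy endpoint gives no status to patients who respond and then leave before 12 months for reasons other than lack of efficacy or an AE, and SAP 5.1 changes how rescue counts without listing the change

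*SAP*

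**What the plan says.** **Version 1.** A responder must reach 50,000/µL within 12 weeks of starting active treatment. In the next 12 months there must then be no pair of low visits at least 4 weeks apart without an intervening adequate count unrelated to rescue (Protocol 10.4.1.1, SAP 4.3). The only discontinuations named as failures are these: "Patients who discontinue treatment due to lack of efficacy or to an AE prior to 12 months following achievement of a platelet count" (the threshold is 50,000/µL). SAP 10.1.1 says the endpoint "applies for all patients entering C-935788-049 study" and reports a percentage with an exact 95% interval. SAP 5.3 says only that missing data are not imputed.

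**Version 2.** The protocol has the same limited rule over 12 weeks: "Subjects who discontinue treatment due to lack of efficacy or to an AE prior to 12 weeks following achievement". The SAP widened it, so that failures are "Patients who discontinue treatment or patients who are rescued prior to 12 weeks following achievement". Version 1 was left as it was.

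**Rescue.** Under the protocol, a high count related to rescue cannot interrupt a run of low counts. SAP 5.1 says something broader: "platelet counts taken within 28 days of rescue therapy will be excluded from any platelet count related analyses". It does not say whether the window lies before rescue, after it, or both. SAP 3.5, which lists departures from the protocol analyses, has no entry for this exclusion.

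**Duration endpoint.** Here the SAP does give leavers a rule: "Patients who drop out of the study by the time of database lock while still maintaining a platelet response will be censored".

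**The concern.** Criterion 2 of Version 1 is met when something is absent, namely a qualifying pair of low visits. A patient who stops being observed cannot show such a pair. Protocol 7.9 lists several exits that are neither lack of efficacy nor an AE: subject decision, non-compliance, erroneous enrolment, pregnancy and loss to follow-up. Treatment may also end at commercial availability. The plan classifies none of these for Version 1, so the coding could be settled after the data are seen.

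The rescue exclusion raises a related problem. Version 1 has no rule that rescue is a failure, and rescue is permitted only at counts below 50,000/µL (Protocol 7.4). Deleting all counts near rescue can therefore remove the low visits that would make a patient fail.

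Version 1 is the only version of the primary efficacy endpoint that covers all patients. Its percentage will be read as the 12-month sustained response rate.

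**Working it through.** The plan states no sample size calculation or expected rate, so there is no figure to reproduce. The check applies the rules to patient sequences and then shows a range of sizes.

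**1. Early leaver.** One count of 55,000/µL at Day 30, then consent withdrawn and no further data. Criterion 1 is met. There is no pair of low visits, so criterion 2 is not violated, and the exit reason is not a named failure. On the literal rule the patient is a responder.

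**2. Rescue, failure to success (Example A).** The patient has responded earlier, is low at Day 120, rescued at Day 124, still low at Day 150, and at or above 50,000/µL from Day 180.
- Protocol: two low visits, 150 − 120 = 30 days apart, nothing adequate between them. Failure.
- SAP 5.1: 150 − 124 = 26 days, so the Day 150 count is deleted and no pair remains. Success, whether the window is after-only or two-sided.

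**3. Rescue, success to failure (Example B).** The patient is low at Day 30, rescued at Day 40, at 80,000/µL on Day 60, and at 60,000/µL from Day 90.
- Protocol: criterion 1 carries no rescue condition, so Day 60 counts and falls within 84 days. Success.
- SAP 5.1: 60 − 40 = 20 days, so Day 60 is deleted. The next adequate count is at Day 90, after Day 84. Failure.

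**4. Size of the early-leaver gap.** Coding k leavers as responders rather than failures adds k/N. One patient at N = 150 (the planned maximum) is 1/150 = 0.67 points. The table assumes 20% true responders; k and N = 100 are also assumptions. Intervals are Clopper-Pearson 95%.

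| k | N = 150 | N = 100 |
|---|---|---|
| 0 | 30/150 = 20.0% (13.9–27.3) | 20/100 = 20.0% (12.7–29.2) |
| 3 | 33/150 = 22.0% (15.7–29.5) | 23/100 = 23.0% (15.2–32.5) |
| 8 | 38/150 = 25.3% (18.6–33.1) | 28/100 = 28.0% (19.5–37.9) |
| 15 | 45/150 = 30.0% (22.8–38.0) | 35/100 = 35.0% (25.7–45.2) |

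If leavers are excluded instead, k = 3 gives 30/147 = 20.4% (14.2–27.8) and k = 15 gives 30/135 = 22.2% (15.5–30.2). As bias against the truth, the table shows upper bounds, because some leavers would have stayed in response.

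**5. Size of the rescue exclusion.** With visits every 30 days, one rescue removes on average about 28/30 = 0.93 visits if the window is after-only and 56/30 = 1.87 if two-sided. A simulation used 12 assumed settings of 8,000 patients each:
- log-normal counts in thousands, mean log 3.4 or 3.7, between-patient SD 0.6, within-patient SD 0.5;
- rescue 0–14 days after a visit below 20 thousand (probability 0.3 or 0.6) or below 30 thousand (0.6);
- counts doubled for 14 days or tripled for 28 days after rescue.

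Against the literal protocol rule, Version 1 moved by −0.4 to +1.0 points with an after-only window and by +0.1 to +4.7 with a two-sided one. In the eight settings with the trigger below 20 thousand, the after-only change was within 0.1 point and the two-sided change at most 0.8.

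**6. Do other planned outputs correct this?** SAP 10.2.1 analyses duration in "all C-935788-049 primary efficacy endpoint version 1 responders". A leaver is censored there, so the Kaplan-Meier curve does not drop. The minimum in the descriptive summary would show a short duration. The 25th percentile would fall below about 12 months only once leavers are about a quarter of coded responders; with 30 true responders, 8/38 = 21.1% and 10/40 = 25.0%, so from about k = 10. Appendix 14.2 ends response at "the first use of rescue therapy after first achieving a platelet count of at least" the threshold, but for durations only. Appendix 14.1 is redacted and cannot be judged.

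**The case against.** The strongest case against has five parts.

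- **The text does not count leavers as responders.** A programmer could require the 12 months to be observed, and the no-imputation rule is compatible with exclusion. This stands. A reader might infer that the SAP expressly codes early leavers as sustained responders. It does not: their status is open, and responder is only the literal reading. Three available codings are still a defect in a primary efficacy endpoint.
- **Version 1 is meant to describe efficacy on active treatment, and its rule comes unchanged from the protocol.** Penalising only drug-related exits fits that purpose, and a stricter rule in the 12-week paired Version 2 does not prove Version 1 wrong. This is fair, but the purpose statement still does not say how an incomplete 12-month window is counted.
- **Other outputs disclose the problem.** Discontinuation reasons (SAP 7.0), counts by visit in Version 1 responders (SAP 10.3), rescue use (SAP 12.5) and listings would let a reader bound k. They do not define or correct the reported percentage.
- **The sizes are assumed.** This stands. In addition, prior-fostamatinib patients who responded by Week 12 and completed Week 24 bring at least 24 − 12 = 12 weeks of follow-up, which shortens the period they can leave unclassified.
- **The 28-day window partly makes operational a protocol phrase that was never defined.** This is true for high counts after rescue. Deleting low counts goes further than the protocol. A reader might infer that the exclusion inflates the response rate; Example B and the after-only simulation show that the direction is not fixed.

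**Conclusion.** Both parts hold as gaps in the rules, and both should be fixed.

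For early leavers, the conclusion rests on the wording alone: only two discontinuation reasons are failures, no follow-up is required, and all patients entering the extension are covered. The effect is k/N, or 0.67 points per patient at N = 150. The value of k cannot be taken from the documents and may be zero. The gap concerns only leavers who reached 50,000/µL within 12 weeks and had not already had a qualifying pair of low visits.

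For rescue, SAP 5.1 is an unlisted change that can reverse a patient's status in either direction. The net effect is of uncertain sign and probably small if the window runs only after rescue. It could be larger if the window is two-sided, but that depends on assumed rescue frequency.

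A reader might infer that the study's main conclusion is at risk. The documents do not support that: the primary objective is safety, efficacy is secondary, and Version 1 is descriptive with no hypothesis test.

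**What to change.** **SAP 4.3.** Count as a Version 1 non-responder any patient who discontinues treatment for a non-administrative reason before 12 months after first reaching 50,000/µL, in line with the SAP's discontinuation rule for Version 2. Report the result under the protocol rule alongside.

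**Administrative cut-off.** State in advance the status of patients whose 12 months are cut short by commercial availability or database lock, and report a Kaplan-Meier 12-month estimate that censors them. They need not be counted as failures.

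**SAP 5.1.** For Version 1 and the main duration endpoint, state that the 28-day window runs after rescue, exclude only counts of at least 50,000/µL within it, and keep counts below 50,000/µL. This follows the protocol's rescue wording for the intervening visit. Applying it also to first achievement goes beyond that wording, because criterion 1 has no rescue condition; Example B would then be a failure. In the simulation this rule gave rates 0.0 to 0.5 points below the literal protocol rule.

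**Sensitivity and record.** Add a Version 1 analysis with rescue counted as failure, and list all these changes in SAP 3.5.

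**Cost.** A few SAP sentences and minor programming. The reported rate may be lower, some patients who leave while still responding will count as failures, and the rate may differ from the interim analysis mentioned in SAP 5.4. Showing the protocol rule alongside keeps the two comparable.

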At the end of Month 1 (approximately Day 30), subjects receiving fostamatinib 100 mg PO *bid* should have the dose escalated to fostamatinib 150 mg PO *bid* if platelet count $< 50,000/\mu\text{L}$ and the study drug is well tolerated (refer to [Section 7.2.1](#)). Conversely, the dose may be reduced at any time to a dose as low as fostamatinib 100 mg PO *qd* if dose-limiting AEs are observed as

defined by this protocol (see Section 7.2.2 and Appendix 1, Appendix 2, Appendix 3, and Appendix 4).

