7.1 Treatment Period

7.1.1 Enrollment (Day 1)

Subjects must be willing to sign and date an Institutional Review Board (IRB)/Independent Ethics Committee (IEC) approved informed consent form (ICF) prior to participating in any study-specific procedure activities. Subjects will retain their same Subject ID number as per Study C-935788-047 or C-935788-048, as applicable.

Subjects who have completed the Week 24 assessments in the previous ITP study within 7 days of enrollment in the extension study do not need to repeat these same assessments. The assessments performed during the Week 24 visit in the prior ITP study will be used to qualify subject for enrollment in the extension study. The subject must sign the ICF prior to enrollment in the extension study. The following assessments must be performed in order for a subject to be eligible for the extension study.

All local and central laboratory results must be reviewed for eligibility prior to enrollment.

- Inclusion/Exclusion Criteria
- SF-36, (must be administered prior to any other study specific procedures (refer to [Appendix 5](#))
- Physical examination, vital signs, and KPS (refer to [Error! Reference source not found.](#))
- Concomitant medications
- Bleeding Assessments by ITP Bleeding Scale (IBLS) (refer to [Appendix 7](#))
- 12-lead electrocardiogram (ECG)
- Complete blood count (CBC) with differential and reticulocyte count
- Platelet count (performed at institutional or local lab)
- Serum chemistry
- Immunoglobulin levels
- Urinalysis
- Pregnancy test (for females of childbearing potential)
- AEs

Table 2: Schedule of Study Procedures

	Day 1 Screen/ Enrollment^a	End of Month 1 (± 3 days)	Months 2–18 (± 3 days)	Months 19–60 (± 1 week)	Follow-up (± 7 days)ⁱ
Informed consent	X				
Inclusion/Exclusion	X				
Physical exam/KPS	X	X	monthly	every other month	X
Concomitant medications	X	X	monthly	every other month	X
Vital signs ^b	X	X	monthly	every other month	X
Bleeding assessment ^c	X	X	monthly	every other month	X
ECG	X				
Hematology ^d	X		monthly	every other month	X
Platelets	X	X	monthly	every other month	X
Serum chemistries (including LFTs) ^e	X		Months 4, 8, 12, 16	every other month	X
LFTs only ^f			monthly (in months full serum chemistries not done)		X
Immunoglobulin levels	X				X
Urinalysis	X		Months 4, 8, 12, 16	every 4 months	X
Urine pregnancy test ^g	X		every other month	every other month	
SF-36 ^h	X		Month 12		
AEs	X	X	monthly	every other month	X
PK			Month 2		

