7.1.2 Treatment Visits

The treatment period begins at the time of enrollment and may continue up to a total of 60 months. Over the course of the study, subjects will be expected to visit the clinic monthly for the first 18 months, followed by every 2 months for the remainder of the study. Assessments including platelet counts will be performed to evaluate the safety and efficacy of fostamatinib, and to determine if a dose adjustment is required. All visits are determined by the date of enrollment and should occur within the windows specified (refer to Table 2 for the complete schedule of study procedures).

[figure not shown]
Study drug accountability will be performed at each visit. New bottle of fostamatinib will be dispensed using the IWRS at each visit. Used bottles will be returned for accountability. At the final visit of the treatment period, final study drug accountability will be performed.

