## 12.5 Rescue Therapy

A rescue therapy event is defined based on the medication administration start date. Two or more rescue medications started on the same day are counted as one rescue therapy event. Only rescue medications administered on or after the first dose of study drug in the present study are included.

The number of rescue therapy events per patient will be summarized using descriptive statistics for the following:

- Placebo patients of the C-935788-047/C-935788-048 study who received rescue therapy prior to Week 10 (Day 73)
- Placebo patients of the C-935788-047/C-935788-048 study who received rescue therapy after Week 10

The number and percentage of patient who received any rescue therapy in the present study will be summarized for

- the placebo patients of the C-935788-047/C-935788-048 study who received rescue therapy prior to Week 10 (Day 73)
- the placebo patients of the C-935788-047/C-935788-048 study who received rescue therapy after Week 10,
- all patients in C-935788-049 study

In addition, the number of patients who received any rescue therapy will be summarized using counts and percentages, and the number of rescue therapy events per patient for all patients who

received any rescue therapy will be summarized using descriptive statistics. These analyses above will be conducted by prior study treatment group and overall.

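### Version 2 maintenance is counted in exact days on a monthly visit grid, so the SAP's only hypothesis test depends on visit timing as well as on treatment

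*SAP*

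**What the plan says.** SAP 4.3 applies one Version 2 rule to both periods of the same patient ("placebo treatment in the prior study and fostamatinib treatment in the present study"). The patient must reach 50,000/µL within 12 weeks. Maintenance is then "defined as no two visits, at least 4 weeks apart, with a platelet count" below 50,000/µL and no intervening high count unrelated to rescue, "within a period of 12 weeks following initial achievement of the target platelet count". Discontinuation or rescue within those 12 weeks is also a failure.

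On timing in the extension, Protocol 7.1.2 states that "subjects will be expected to visit the clinic monthly for the first 18 months". Protocol Table 2 allows ±3 days at Month 1 and thereafter (column head "Months 2–18 (± 3 days"). Protocol 5.1 puts Month 1 at about Day 30 ("At the end of Month 1 (approximately Day 30").

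SAP 10.1.2 compares the periods with a "2-sided exact McNemar's test with a significance level of 0.05". SAP 3.5 drops the protocol's other McNemar test and its one-sample t-tests, so this is the only hypothesis test that the SAP describes. Its Table 3 labels the placebo-period rows as stable responders and the extension columns as Version 2 responders.

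The 047/048 visit schedule is not in the documents. They mention only isolated time points such as Weeks 10, 12 and 24; SAP 12.5, for example, groups placebo patients "who received rescue therapy prior to Week 10 (Day 73". Nothing says how a difference in visit frequency is to be handled.

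**The concern.** A rule that needs two low counts at least 28 days apart inside 84 days can detect a loss only as well as the visit grid allows. If the grids differ, the same platelet course can be a success in one period and a failure in the other. McNemar's test uses only the patients whose status changes between periods, so a status change produced by the calendar enters the test in the same way as one produced by the drug. Separately, a response seen at one or two visits and then lost for good does not fit the plain meaning of a sustained stable response.

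**Working it through.** The plan gives no power or error-rate figure for Version 2 (SAP 3.4), so there is nothing to reproduce. I counted visits instead.

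**Inputs.** Window 84 days and minimum spacing 28 days (SAP 4.3); monthly visits (Protocol 7.1.2); ±3 days (Protocol Table 2); month of about 30 days (Protocol 5.1). Assumptions: first response at a scheduled visit, no unscheduled counts, no rescue or discontinuation, and 047/048 visits every 1, 2, 3, 4 or 6 weeks.

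**1. Visits in the window.** After achievement, visits fall nominally at +30, +60 and +90, so two lie within 84 days. With visit offsets d from −3 to +3, all equally likely, the third visit is inside only if 90 + d3 − d0 ≤ 84. That needs d3 − d0 = −6, which is 1 of 49 pairs (2.0%).

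**2. Spacing of the two in-window visits.** The gap is 30 + d2 − d1, and it is below 28 when d2 − d1 ≤ −3. That is 4 + 3 + 2 + 1 = 10 of 49 pairs (20.4%). Two low counts then do not meet the 4-week condition. Allowing for the rare third in-window visit, a patient low at every visit after one high count passes in (10/49) × (48/49) = 20.0% of combinations.

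**3. Permanent loss on day L, nominal days.** Failure requires L to be no later than a visit that precedes the last in-window visit by at least 28 days.

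| Grid | In-window visits | Latest loss scored as failure |
|---|---|---|
| 049, 30-day month | +30, +60 | day 30 |
| 049, 28-day month | +28, +56, +84 | day 56 |
| Placebo, every 1, 2 or 4 weeks (assumed) | 12, 6 or 3 | day 56 |
| Placebo, every 3 or 6 weeks (assumed) | 4 or 2 | day 42 |

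With a 30-day month, a loss between about day 31 and day 42 to 56 passes in 049 and fails in the placebo period. If response durations were exponential with median m days (an assumption), the share of achievers losing response in the gap is 2^(−30/m) − 2^(−56/m). That is 0.707 − 0.524 = 18% for m = 60 and 0.945 − 0.899 = 5% for m = 365.

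**4. Whole endpoint.** Denser visits also make achievement easier. Take an independent chance p of a high count at each visit, and the visits that fall within 84 days. Monthly: achievement and maintenance each have probability 1 − (1−p)². Every 2 weeks: achievement is 1 − (1−p)⁶, and maintenance means no three consecutive lows in six visits. Every 4 weeks: achievement is 1 − (1−p)³, and maintenance means no two consecutive lows in three visits.

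| p | Monthly | Every 2 weeks | Every 4 weeks |
|---|---|---|---|
| 0.1 | 0.190 × 0.190 = 0.036 | 0.469 × 0.052 = 0.025 | 0.271 × 0.109 = 0.030 |
| 0.2 | 0.360 × 0.360 = 0.130 | 0.738 × 0.181 = 0.133 | 0.488 × 0.232 = 0.113 |
| 0.3 | 0.510 × 0.510 = 0.260 | 0.882 × 0.348 = 0.307 | 0.657 × 0.363 = 0.238 |

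Against a 2-weekly grid the sign changes with p.

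**5. Correlated counts, no drug effect.** I simulated AR(1) log counts with median 18,000 to 28,000/µL, between-patient SD 0.4, within-patient SD 0.5 to 0.7 and 2-week correlation 0.3 to 0.9. The difference in Version 2 rate, 049 minus placebo period, in percentage points:

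| Visit timing | Placebo every 2 weeks | Placebo every 4 weeks |
|---|---|---|
| Exact days in both | −0.9 to +0.4 | +0.4 to +2.4 |
| ±3 days in both | −5.1 to −0.1 | −3.7 to −0.4 |
| ±3 days in 049 only | +0.3 to +3.2 | +0.9 to +5.7 |

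The sign depends on the spacing and windows assumed for 047/048.

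**The case against.** Four points deserve weight.

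- **Direction.** A reader might infer that the rule favours fostamatinib, because maintenance alone is easier to pass on a monthly grid than on a denser one. The documents do not support that for the tested endpoint. Steps 4 and 5 show that easier achievement and the unknown 047/048 windows can cancel or reverse the gap. Two-weekly placebo visits are only a guess from the mention of Weeks 10 and 12.
- **Error rate.** No inflation of the McNemar test is shown. Granting a gap of 1 to 3 points for the drug and reverse discordance of 1 to 5%, the two-sided exact test rejects in 0.0 to 3.2% of trials with an assumed 30 to 50 placebo rollovers, and in at most about 5.7% with 75.
- **Same rule, with safeguards.** It would be wrong to say that SAP 4.3 sets unlike rules. The text is identical for both periods, and rescue or discontinuation within 12 weeks already fails the patient. Nor does every course that is high at +30 and low from +60 fail in the placebo period: a loss on days 57 to 60 passes there too. What the SAP does leave open is whether the stable-responder rows of Table 3 use the Version 2 rule.
- **Calendar.** Protocol 5.3 and 7.3 equate 3 months with 12 weeks. On a 28-day month a visit lands on +84 and the nominal gap against a 1-, 2- or 4-weekly placebo grid closes. With ±3 days it does not fully close: the third visit is then inside in 57.1% of combinations, and a patient low at every later visit still passes in 18.4%.

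The first three limit what can be claimed about bias. None removes the dependence on visit timing.

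**Conclusion.** The concern holds as a weakness in the Version 2 definition, not as a demonstrated bias. With a 30-day month, the 84-day window normally contains two extension visits. Without rescue or discontinuation, a response lost for good after about day 30 counts as sustained, and in about 20% of visit-window combinations so does one followed only by low counts. Under every placebo-period interval tried (1 to 6 weeks), permanent losses between about day 31 and day 42 to 56 are scored differently in the two periods. The SAP's only hypothesis test therefore reflects visit timing as well as treatment. The net effect under no drug effect ranged from about −5 to +6 points across the assumed schedules and windows, so neither its sign nor its size can be stated until the 047/048 schedule is given. These figures assume equally likely visit offsets, response first seen at a scheduled visit, and no unscheduled counts. The primary objective is safety, which this point does not touch.

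**What to change.** In SAP 4.3 and 10.1.2:

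- Score both margins of Table 3 by the Version 2 rule, and relabel the placebo-period rows accordingly.
- Use matching nominal visits. In 049, use Months 1, 2 and 3 for achievement and the next three monthly visits for maintenance. In the placebo period, use Weeks 4, 8 and 12 and then the next three 4-weekly visits, taking the count nearest each nominal day. The latest case ends at Week 24, inside the parent study.
- Treat consecutive nominal monthly visits as at least 4 weeks apart.
- Keep the existing failure rule for rescue and discontinuation.
- State the 047/048 visit schedule and windows, and confirm that the 4-weekly grid fits them.
- Report the exact 84-day rule as a sensitivity analysis.

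Under step 4's independence model the two periods become identical by construction (for p = 0.2, 0.488 × 0.232 = 0.113 in both). In the correlated simulation they came within about 0.5 point under no effect, with visit jitter included.

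The cost is SAP wording and one reprogrammed derivation, with no new data. Some parent-study counts go unused in the main score, and the fostamatinib Version 2 rate may be slightly lower.
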